## Form A

IRB #	STU -----
-------	-----------

SC will attempt to contact patients who cannot be reached the following business day.

Patients who do not complete pre-appointment survey will be excluded from study but will continue with scheduled genetic counseling appointment as standard of care.

Pre-appointment survey completion status and survey completion method will be recorded in RedCap by SC.

Genetic Counseling and Genetic Testing. Patients who are unable to watch the educational video prior to, or during their genetic counseling visit will be excluded from the study. They will still continue with their appointment, but not through the study. Patients excluded for this reason will be recorded in RedCap by SC.

Sample failure and test completion status will be recorded in RedCap by SC. Failure to complete testing will not exclude patient from the study itself.

Post-Appointment Survey and Study Incentive. SC will send post-appointment survey within 24 hours of GC appointment. A Spanish version of the survey will be sent to Spanish-speaking patients.

The post-appointment survey will consist of the Multi-dimensional Model of Informed Choice (MMIC) assessment, the Genetics Outcome Scale (GOS) and the Genetic Counseling Satisfaction Scale (GCSS).

SC will monitor survey completion status. Those with incomplete post-appointment surveys will receive reminder two business days post-appointment and will be offered option to complete the survey via telephone with SC.

If patient is not reached, SC will attempt to contact patient the following day (three business days post-appointment).

Those with incomplete surveys one week after the genetic counseling appointment will be excluded from study. This data will be recorded in RedCap.

Those who complete study surveys will be sent a \$15 gift card electronically.

Location/Setting. For IPGC, patients will be seen within PHHS/JPS clinics. Spanish translation services are provided through PHHS and JPS for patients in their institutions. TGC patients will not be required to be in a certain environment, but we anticipate they will be in their homes or workplace in a secure, private location. GCs will either be in a HIPPA compliant setting offsite or within a UTSW workspace for TGC visits.

Data Analysis. Our primary study outcomes are to compare change in knowledge pre and post visit (through MMIC knowledge questions), patient satisfaction with GC visit after completion (GCSS) and genetic counseling visit completion rate between IPGC and TGC. Secondary objectives include comparison of empowerment score (GCOS), informed choice (MMIC scale), genetic testing completion, and cancelation/failure rates between the arms.

To evaluate intervention effects, we will conduct univariable and multivariable analysis for comparisons of each outcome of interest between intervention (TGC) and control group (IPGC). For the survey data, we will examine the data from each survey as well as total score or overall index of multiple questionnaires and compare them between the two study arms. We will perform linear regression models for continuous outcomes (e.g., total score of questionnaires) and logistic regression models for binary outcomes that are based on binary response (e.g., visit completion rates, test cancelation/failure and test completion rates). To compare binary outcomes between arms (such as visit completion rate), we will test by comparing rates of each arm via Chi-squared analysis and control for potential confounders. Potential covariates under consideration (e.g., age, race, sex, language, etc.) will be assessed as necessary and adjusted in multivariable models accordingly. We will evaluate whether there is any evidence of multi-collinearity issues among these variables to be adjusted in the model. Possible effect modifiers of intervention effects will be also evaluated by testing interactions (e.g., sex) and addressed to develop the final multivariable models, as well as reporting the intervention effect stratified as an effect modifier. Underlying assumptions of aforementioned regression models including linearity of associations will be also evaluated. We will examine dropouts or missing data to be able to identify accurate missing data mechanisms and select the best statistical approach. All analyses will be performed using SAS 9.4 (SAS Institute Inc, Cary, NC) at a statistical significance level of  $p=0.05$ .

We anticipate a post-enrollment dropout (failure to complete the surveys) rate of 30% given our work with the underserved population. We plan to enroll 280 patients at a 1:1 ratio per arm (100 individuals enrolled per arm), expecting 200 to complete measured responses. We will monitor the dropout rate after the initial 50 individual responses are completed and adjust accrual for study-specific dropout until we have 200 participants' complete measured responses. With 200 patients we will enroll, we can detect mean differences of 0.398 standard deviation (SD) between two study arms with 80% power at a significance level of 0.05 (Table 1). For example, assuming SD of 2 for the GCSS, we will be able to detect a minimum difference of 0.8 ( $=0.398*2$ ) between two study arms with 100 participants enrolled per arm. For GCOS, assuming SD of 46.58, we will be able to detect a minimum difference of 18.54 between pre- and post-visit scores. For visit completion as the primary binary outcome variable, we will be able to detect a minimum difference of 18.6% assuming 63% in the control group, e.g., 81.6% (intervention) vs. 63% (control) with 80% power at significance level of 0.05. Of note, previously published outcomes and unpublished internal data will serve as a baseline for the study population.

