#### 1. Purpose and objectives. *List the purpose and objectives:*

The overarching goal of this pilot prospective randomized controlled study is to compare patient-reported and clinical operations outcomes between in-person genetic counseling (IPGC – control) and telephone-based genetic counseling (TGC – intervention) in an indigent English or Spanish-speaking population seeking genetic counseling for hereditary cancer syndromes to create a framework for effective and efficient genetic service delivery in these populations nationally. General genetic education and principles will be conveyed through a standard genetic counseling session including a pre-test education video in both the TGC and IPGC arms. Our primary project objectives are to compare the following outcomes between the IPGC and TGC study arms. Aim 1: Patient reported outcomes – A. Patient satisfaction with genetic counseling visit; B. Knowledge of basic principles of cancer genetics and implications of genetic testing for personal healthcare and relatives. Secondary objectives for this aim are: 1. Patient ability to make informed choice; and 2. Genetic counseling-specific empowerment outcomes. Aim 2: Clinical outcomes – visit completion rate; Secondary objectives are: 1. Genetic testing completion rate; and 2. Genetic testing cancellation/failure rate. We hypothesize that patients in the TGC arm will not have significant differences in knowledge, satisfaction, informed choice or genetic counseling-specific empowerment compared to the IPGC arm. We also expect significantly increased visit completion rate and lower test completion rate in the TGC arm compared to the IPGC arm, but no significant difference in sample failure rate.

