##### a. Background

Similar studies have been performed in primarily non-Hispanic white, above-average income, college-educated, English-speaking populations, but to our knowledge, a study comparing outcomes of TGC and IPGC service delivery models (SDMs) has not been reported in an entirely indigent population with a high volume of Latinx/Spanish-speaking patients. Indigent Populations. Less access to healthcare and hereditary risk assessment are well documented in indigent populations, often composed of ethnic/racial minorities, or geographically isolated and economically underserved groups. 7-9 Barriers include provider paucity, under-recognition of family history risk factors, financial hardship, and other factors. 10- 17 Internet use via mobile technologies has increased access to healthcare information in indigent populations .18, 19 National surveys revealed 91% of families living below the poverty level have some type of internet access, and of Americans earning <\$30,000 annually, 701% owned a smart phone. Review of 2019 internal program data revealed 84-88% of safety-net hospital clinic uninsured/Medicaid patients provided an email address and reported internet connectivity. This access creates an avenue for genetic counselors to reach underserved populations. Genetic Counseling Service Delivery. Some randomized trials comparing outcomes of TGC v. IPGC cancer risk assessment sessions in resource-rich populations showed similar levels of patient satisfaction, knowledge, cancer worry, risk perception, decisional conflict, and motivation to change health-related behavior with similar data for telegenetics (video) studies. In one study, the majority of participants indicated they would not have pursued genetic counseling had TGC not been offered. Need for Project. A majority (89%) report already using a phone for medical discussions. Traditional healthcare infrastructures remain a barrier for indigent patients, and while the rise in telegenetics companies and platforms in a response to the increasing need for remote genetic counseling to

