**Randomization and Scheduling:**

Study coordinator (SC) will monitor referral queue daily

Randomization software (<http://abtesting.ideas42.org/randomize/>) will be used to randomize patients in the referral queue to each study arm (in-person genetic counseling or IPGC/ telephone genetic counseling or TGC). Patients who meet the following exclusion criteria will not be randomized to a study arm. Patients who are excluded from the study will be scheduled for an appointment as per normal clinic protocol by the clinic schedulers.

SC will monitor number of participants per study arm and adjust recruitment accordingly.

Patients who have been randomized to a study arm will be scheduled for IPGC or TGC by schedulers at John Peter Smith (JPS) and Parkland Hospital (PHHS). Schedulers will inform patients of their appointment as per normal clinic protocol. Spanish-speaking patients will be contacted with an interpreter.

Patients who elect alternative service delivery model for genetic counseling than what was assigned after randomization will be excluded from the study. The genetic counseling appointment type will be modified based on patient preference and patient will continue with scheduled visit, but not as part of the study.

SC will record the following data for all referred patients in Research Electronic Data Capture (RedCap), a secure, web-based application for research data: MRN; study arm assigned; genetic counseling appointment date; if patient was excluded from study, and reason for exclusion. The following demographic data will also be tracked: patient's age; patient's sex; patient's race and ethnicity; patient's preferred language; patient's contact information (phone number and e-mail address)

**Study Eligibility Determination and Informed Consent.** One week prior to scheduled genetic counseling appointment, SC will call patient to assess if patient meets study eligibility criteria. Spanish-speaking patients will be contacted with an interpreter.

If SC cannot reach the patient, SC will make second contact attempt the following business day.

Scheduled patients who cannot be reached or do not call back will be excluded from study.

SC will record the following data in RedCap: contact date and outcome; if eligibility criteria were met; if patient was excluded from study, and reason for exclusion.

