If patient qualifies for study, SC will describe study protocol and get verbal consent for study participation using the consent script. All patients will be sent a hard copy of the consent document for their records (available in English and Spanish) electronically along with the study surveys via RedCap.

Patients who decline will be excluded from study. Study participation status will be recorded in RedCap (including reason for declining participation).

Patients who decline to be in the study will be sent an appointment letter and will continue with scheduled genetic counseling appointment as per normal clinic protocol, not as part of the study.

**Pre-Appointment Resources and Survey Completion.** Patients who agree to participate in the study will be sent the pre-appointment survey (Appendix B). A Spanish version of the survey will be sent to Spanish-speaking patients. Surveys will include a hard copy of the consent document that can be downloaded as desired. Survey links will be sent to patients via email. All surveys will be available through REDCap.

The pre-appointment survey will consist of the Multi-dimensional Model of Informed Choice (MMIC) assessment and the Genomics Outcome Scale (GOS).

SC will check pre-appointment survey completion status two business days prior to appointment.

Patients with incomplete pre-appointment surveys will be contacted two business days prior to appointment and will be reminded to complete survey. Patients will be offered the option to complete survey via telephone with SC. Spanish-speaking patients will be contacted with an interpreter.

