**Form A**

IRB #	STU -----
-------	-----------

		
4.d. List ALL other research procedures or components not listed in table 4.b.  The combination of Tables 4b and 4d should account for all of the research procedures that will take place during this study.
 
Consider grouping similar procedures under a single component (e.g., blood work, CT = safety assessments)
		
#	
Research component
 
 
individual procedures
 
 
example:  Eligibility Assessments
 
 
History and physical
 
Questionnaire
 
Laboratory tests
 
 
Add or delete rows as needed
	
Column A  Local Standard Practice Indicate the number of times each procedure will be performed as stipulated in the research plan that would be performed if the participant were not participating in the study.
	
Column B  Research Only  Indicate the number of times each procedure will be performed solely for research purposes (meaning that the participant would not undergo the same number of procedures or would not undergo the procedure(s) at the same frequency if they were not participating in the study)
	
Column D
 
Risks  If you are requesting a Waiver of Informed Consent, complete the table below.
 
List the reasonably expected risks for each procedure or group of procedures under the following categories as appropriate:
 
 
• Serious and likely;
 
• Serious and less likely;
 
• Serious and rare;
 
• Not serious and likely;
 
• Not serious and less likely
 

1	Eligibility Assessments			
	Review inclusion/exclusion criteria		1	Not serious and less likely
2	Questionnaires			
	Pre-visit: MMIC/GOS		1	Not serious and less likely
	Post-visit: MMIC/GOS/GCSS		1	Not serious and less likely
3	Video education viewing			
	Educational video sent to telephone GC patients for viewing prior/during visit	1		Not serious and less likely
	Educational video for in-person GC patients viewed in session	1		Not serious and less likely
4				

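### The post-randomisation exclusion of patients unable to watch the video falls mainly on the telephone arm, so satisfaction and knowledge are compared on differently selected groups

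*Combined protocol and SAP*

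**What the plan says.** Under Randomization and Scheduling in section 4.a, the randomisation software "will be used to randomize patients in the referral queue to each study arm". The eligibility call, consent, pre-appointment survey and visit all come later.

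Under Genetic Counseling and Genetic Testing in the same section: "Patients who are unable to watch the educational video prior to, or during their genetic counseling visit will be excluded from the study". These patients keep their appointment outside the study, and the coordinator records the reason for exclusion in REDCap.

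The video belongs to the counseling package in both arms; section 1 describes a standard session "including a pre-test education video in both the TGC and IPGC arms". Delivery differs. Table 4.d, row 3, lists for one arm "Educational video sent to telephone GC patients for viewing prior/during visit" and for the other "Educational video for in-person GC patients viewed in session".

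Surveys are handled differently from the video. "Survey links will be sent to patients via email", but for an incomplete pre-appointment survey "Patients will be offered the option to complete survey via telephone with SC". The same offer is made for the post-appointment survey. No such fallback is given for the video.

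On access, section 2.a reports from 2019 internal data that "84-88% of safety-net hospital clinic uninsured/Medicaid patients provided an email address and reported internet connectivity".

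**The concern.** Whether a patient can watch the video depends partly on the assigned arm. A telephone patient needs a device and a connection. An in-person patient needs only to attend. Two patients with the same lack of internet are therefore treated differently: the in-person patient can see the video in clinic, answer the surveys by telephone and stay in, while the telephone patient is dropped after being randomised and having consented. Randomisation no longer guarantees that the groups compared are alike in connectivity, or in whatever goes with it.

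The analysis plan does not repair this. The Data Analysis text names no as-randomised population and no analysis that includes these patients. The covariates it gives as examples (age, race, sex, language) do not include connectivity. The 30% dropout allowance covers survey non-completion only. Accruing until 200 participants have complete responses restores numbers but leaves the selection in place.

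Section 1 hypothesises no significant difference in knowledge or satisfaction. If poorly connected patients do worse by telephone, removing them from that arm could hide a real deficit in the population the trial is meant to inform.

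**Working it through.** **Plan's own figure.** With 100 per arm, two-sided 0.05 and 80% power, the exact two-sample t calculation gives a detectable difference of 0.3981 SD. The normal approximation gives (1.960 + 0.842) × √(2/100) = 0.396 SD. The stated 0.398 SD is reproduced and serves as the yardstick.

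**Inputs.**
- Telephone arm: 280 enrolled at 1:1 gives 140 (sample-size text; the same sentence also mentions 100 per arm, but the fractions below do not depend on this).
- Telephone attendance: 81.6%, the plan's illustrative intervention rate.
- f, the share of attending telephone patients unable to view the video: 12-16%, the complement of 84-88%. This is a proxy and assumes that access is unrelated to attendance.
- D, the mean score gap in SD between patients able and unable to view. The documents give none, so 0.25, 0.5 and 1 are assumed.

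**Patients removed.** Only attenders have post-visit scores to lose. Attenders: 140 × 0.816 = 114.2. Removed: 114.2 × 0.12 = 13.7 to 114.2 × 0.16 = 18.3, so about 14-18. In person the expected number is close to none.

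**Bias.** If viewers average m and non-viewers m − D, the whole arm averages (1 − f)m + f(m − D) = m − fD. Analysing viewers alone shifts the telephone mean by fD. With no true difference and 100 analysed per arm, the chance of a significant result is P(|Z + fD/√(2/100)| > 1.96).

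| Assumed D (SD) | Bias fD (SD) | Share of 0.398 SD | False-positive rate (nominal 5%) |
|---|---|---|---|
| 0.25 | 0.03-0.04 | 8-10% | 5.5-5.9% |
| 0.5 | 0.06-0.08 | 15-20% | 7.1-8.7% |
| 1 | 0.12-0.16 | 30-40% | 13.6-20.5% |

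At D = 0.5 the bias is 0.12-0.16 satisfaction points (SD 2) or 0.30-0.40 knowledge points (SD 5.03, with D read as a gap in pre/post change). To equal the detectable difference, D would have to be 0.398/0.16 = 2.5 to 0.398/0.12 = 3.3 SD.

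**Visit completion.** The plan does not say whether excluded patients leave this denominator. If they do, a true 81.6% becomes (114.2 − 13.7)/(140 − 13.7) = 79.6% to (114.2 − 18.3)/(140 − 18.3) = 78.8%. That works against the telephone arm. If they stay in the denominator and their visits count, there is no effect.

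**The case against.** A reader might infer that the rule removes telephone patients only and leaves an unfiltered in-person arm. The documents do not support that. Both arms lose patients who cannot be reached, decline, choose the other mode or leave a survey incomplete. Survey links go by e-mail in both arms, with the telephone option offered only at the reminder stage. An in-person patient could also occasionally miss the video. What stands is narrower: this particular rule falls mainly on one arm.

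A reader might also infer that the bias must favour telephone counseling. That is plausible but not shown. No document gives a score gap. Knowledge is analysed as a pre/post change, so a stable difference in level would partly cancel; satisfaction, measured only after the visit, lacks that protection. Any effect on visit completion would run the other way.

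The 12-16% may be too high. Its complement requires both an e-mail address and connectivity, and lacking an e-mail address is not inability to watch. Section 2.a also cites 91% of families below the poverty level with some internet access, hence 9% without; that would be 114.2 × 0.09 = about 10 patients. Unconnected telephone patients may already have left by electing in-person counseling.

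Most important, Randomization and Scheduling announces a list of exclusion criteria that is not in the text available for review. If it requires internet access of both arms, most of the asymmetry disappears. Nothing in the available text states such a requirement.

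Finally, the video is part of the package in both arms and these exclusions are recorded. A viewers-only comparison is a recognisable choice for a pilot, and the exclusions could be reported by arm. But reporting them does not recover post-visit scores that were never collected.

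**Conclusion.** The concern holds in a limited form. The video rule is a post-randomisation exclusion whose trigger depends on how the assigned arm receives the video, and no planned analysis keeps the excluded patients. That follows from section 4.a and table 4.d without any assumption about numbers, subject to the unseen exclusion list.

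The size does rest on assumptions. With the 12-16% proxy, about 14-18 of some 114 attending telephone patients would be removed, and the bias would be 0.03-0.16 SD for score gaps of 0.25 to 1 SD. Even the top of that range is under half the detectable difference, but it is enough to disturb the error rate, and further accrual would not reduce it. The direction is not established. The shift in visit completion, about 2 to 3 percentage points, arises only if excluded patients leave the denominator.

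**What to change.** Delete the video exclusion and replace it with a retention rule: *Consented patients who do not watch the video stay in their assigned arm for all outcomes and are sent the post-appointment survey; a visit they attend counts as completed.* Record whether the video was viewed, yes or no, report it by arm, and run the viewers-only comparison as a supportive analysis. The main comparison then keeps these patients as randomised.

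The cost is a wording change and one REDCap field; the coordinator already records these exclusions. The small downside is that some telephone patients in the main analysis will not have seen the video. The change should precede data collection, because post-visit scores not collected at the time cannot be recovered later.

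Adding a new internet-access criterion before randomisation is not recommended as a substitute. Patients are randomised from the referral queue before the eligibility call, so it could need an extra screening step, and it would narrow the population the trial is meant to study.

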**Form A**

IRB #	STU -----
-------	-----------

*Table 1.* Summary of instrumentation with objectives, measures and distribution plan. Summary of data analysis plan per primary and secondary objectives. Minimum detectable difference between two study arms with 80% power at 2-sided significant level of 0.05 (n=100 per arm)

Aims	Objective Type	Instrumentation	Outcome Measure	Distribution	Minimum Detectable Effect Size at 80% power
Aim 1: Patient Satisfaction	Primary	GCSS	Whole scale score	Post	+/-0.8 points, assuming SD = 2 
Aim 1: Knowledge	Primary	MMIC (8 knowledge questions)	Measure score difference from pre/post	Pre and Post	+/-2 points, assuming SD = 5.03
Aim 1: Informed Decision Making	Second	MMIC (entire measure)	Measure score difference from pre/post	Pre and Post	n/a
Aim 1: GC-specific empowerment	Second	GOS	Measure score difference pre/post	Pre and Post	+/-18.54 points, assuming SD = 46.58 
Aim 2: GC visit completion	Primary	Database query	Proportion of visits scheduled and completed	n/a	18.6%, assuming 63% in control group 
Aim 2: Genetic test completion	Second	Database query	Proportion of genetic tests completed w/n 60d of visit	n/a	19.4%, assuming 77.4% in control group 
Aim 2: Genetic test cancellation/failure	Second	Database query	Proportion of genetic tests initiated compared to tests canceled/failure	n/a	15%, assuming 9% in control group 

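### Satisfaction and post-visit knowledge are compared only among patients who attended, although telephone counselling is expected to raise attendance, and no analysis addresses the resulting selection

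*Combined protocol and SAP*

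**What the plan says.** - **Timing (section 4.a, Post-Appointment Survey and Study Incentive).** "SC will send post-appointment survey within 24 hours of GC appointment". The survey contains the MMIC, the GOS and the GCSS. The rule for non-completers is: "Those with incomplete surveys one week after the genetic counseling appointment will be excluded from study". No survey is described for patients who miss the visit.
- **Outcomes (section 4.a, Data Analysis; Table 1).** The primary outcomes are "patient satisfaction with GC visit after completion (GCSS"), knowledge, for which the plan will "compare change in knowledge pre and post visit (through MMIC knowledge questions"), and visit completion. Table 1 gives the knowledge measure as "Measure score difference from pre/post"; the GCSS is given after the visit only.
- **Expected attendance (section 1).** "We also expect significantly increased visit completion rate and lower test completion rate in the TGC arm compared to the IPGC arm". No size is given. For knowledge, satisfaction, informed choice and empowerment, the hypothesis is that the arms will not differ significantly.
- **Size of the attendance difference (section 4.a, sample size).** "we will be able to detect a minimum difference of 18.6% assuming 63% in the control group, e.g., 81.6% (intervention) vs. 63% (control"). This is a detectable difference, and Table 1 lists it under that heading.
- **Analysis (section 4.a, Data Analysis).** Linear regression for continuous outcomes, with covariates such as age, race, sex and language adjusted for where needed. Missing data will be examined before an approach is chosen. No analysis population, estimand or sensitivity analysis for unequal attendance is named.

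**The concern.** Randomisation makes the arms comparable as assigned. It does not make attenders comparable once the mode of counselling affects who attends. If the telephone brings in patients who would have missed an in-person visit, the telephone attenders include them and the in-person attenders do not. A regression of GCSS or knowledge change on arm then mixes the effect of mode with the difference in who was counselled. Full survey response from every attender would not remove this.

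It matters more here because the survey hypothesis is one of no significant difference. Selection could offset a true deficit with telephone counselling, and the null result would be read as confirmation. It could equally produce a difference where mode has no effect.

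**Working it through.** **1. The plan's figures reproduce.** With 100 per arm, two-sided 0.05 and 80% power, the t-test detectable difference is 0.3981 SD (plan: 0.398). For 63% against 81.6%, Fisher's exact test has 80.4% power at 100 per arm. The continuity-corrected formula needs 101 per arm; the uncorrected chi-squared test needs 90.

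**2. Share of telephone attenders without an in-person counterpart.** Let p = 0.63 (the plan's control rate) and d = the attendance difference. Assumption: everyone who would attend in person would also attend by telephone. Then share = d / (p + d).

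- d = 0.05: 0.05 / 0.68 = 7.4%
- d = 0.10: 0.10 / 0.73 = 13.7%
- d = 0.186: 0.186 / 0.816 = 22.8%

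The first two values of d are illustrative. The third is the plan's detectable difference.

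**3. Bias.** Let g = the outcome gap, in SD, between these extra attenders and the rest. The documents give no value, so g is assumed. Bias = share × g.

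| Attendance difference | g = 0.25 | g = 0.5 | g = 1.0 |
|---|---|---|---|
| 5 points | 0.018 SD | 0.037 SD | 0.074 SD |
| 10 points | 0.034 SD | 0.068 SD | 0.137 SD |
| 18.6 points | 0.057 SD | 0.114 SD | 0.228 SD |

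At 18.6 points and g = 0.5, the bias is 0.114 × 2 = 0.23 GCSS points, against a detectable 0.8. For knowledge, if g applies to the gain and the plan's SD of 5.03 is used, it is 0.114 × 5.03 = 0.57 points, against a detectable 2. To create the full 0.398 SD from selection alone, g would have to be 0.398 / 0.228, about 1.75 SD.

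**4. Effect on the test at 18.6 points** (noncentral t, 100 per arm, non-centrality = difference / √(2/100)).

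- No true effect: the chance of p < 0.05 is 6.9%, 12.6% and 36.1% for g = 0.25, 0.5 and 1.0, instead of 5%.
- True effect of 0.398 SD with bias in the opposite direction: power falls from 80% to 67%, 52% and 22%.

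**5. Worst-case trimming bounds.** For a normal score, removing the top or bottom share q of the telephone attenders moves their mean by φ(z) / (1 − q), where z is the (1 − q) quantile.

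- q = 7.4%: 0.139 / 0.926 = 0.15 SD
- q = 13.7%: 0.219 / 0.863 = 0.25 SD
- q = 22.8%: 0.302 / 0.772 = 0.39 SD

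**6. Sample size is not the problem.** With equal response among attenders, 200 completers split as 200 × 0.63 / 1.446 = 87 and 200 × 0.816 / 1.446 = 113. The detectable difference becomes 0.402 instead of 0.398 SD. Accruing to 200 completers, or adjusting recruitment by arm, evens out the numbers but leaves the selection in place.

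**The case against.** **The plan does not forecast 18.6 points.** A reader might infer from "e.g., 81.6% (intervention) vs. 63% (control) with 80% power at significance level of 0.05" that this difference is expected. It is the smallest difference the trial could detect, offered as an example. Only a significant increase is predicted, so smaller differences must be shown too, and the bias is then smaller. This stands.

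**63% may not describe the survey participants.** Table 1 defines completion over scheduled visits. Survey participants have already been reached, consented and completed a pre-visit survey. The plan allows 30% dropout in all, whereas 63% attendance alone loses 37% of the in-person arm. Averaged over arms at the example rates, attendance is (63 + 81.6) / 2 = 72.3%, so 70% completion would need 0.70 / 0.723 = 97% response among attenders. This stands: attendance among participants could be higher than 63%, and the shares above are illustrations.

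**Knowledge is a change score.** Differences in starting level largely cancel within patients, so less prepared attenders do not by themselves bias it. This stands. Bias needs a difference in how much patients gain, and the documents do not settle whether there is one. GCSS has no baseline and no such protection.

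**The plan already promises covariate adjustment and a review of missing data.** This helps only in part. Adjustment is discretionary and not directed at attendance, and the missing-data method is left open. Satisfaction with a visit that did not happen is undefined, so a missing-data method cannot recover it.

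**The absence of a survey for non-attenders is inferred.** For GCSS it follows from the definition. For MMIC and GOS it follows from the appointment-based timing and the one-week exclusion; no sentence says so outright. If non-attenders are surveyed, the plan should say so.

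**This is a pilot.** That is a fair reason for a proportionate remedy. It is not a reason to leave the population unstated when the aim is a framework for national service delivery.

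**Conclusion.** The concern holds as a structural weakness of unknown size. Two primary comparisons condition on attendance, a post-randomisation event that is itself a primary outcome and is predicted to differ by arm, and the plan names no population or sensitivity analysis for this.

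Under the assumptions shown, a 0.5 SD gap gives a bias of 0.04, 0.07 or 0.11 SD for attendance differences of 5, 10 or 18.6 points. At 18.6 points, gaps of 0.25 to 1.0 SD give 0.06 to 0.23 SD, against a detectable 0.398 SD. These figures rest on the plan's 63%, on everyone who would attend in person also attending by telephone, and on an assumed gap. For knowledge, the gap must be in gain.

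A reader might infer that the comparisons are already shown to be biased, or that the 0.39 SD bound measures the likely error. The documents support neither: they give no gap, and the bound is the extreme case at one illustrative attendance difference. The change should be made, but the weakness does not invalidate the design.

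**What to change.** In section 4.a, Data Analysis, keep the comparison of attenders and add three things.

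1. **Population.** State that the satisfaction and knowledge conclusions apply among patients who attended.
2. **Weighted sensitivity analysis.** Weight by the inverse of the probability of attending and completing the survey, modelled separately by arm from pre-visit MMIC, pre-visit GOS, age, sex, race and language. All are already collected before the visit. Weighting corrects only for these measured predictors, and only back to patients with a completed pre-visit survey; it does not reach those excluded earlier after randomisation.
3. **Trimming bounds.** Report bounds that trim the arm with higher attendance, and state the assumption in step 2 of the working. If survey response among attenders also differs by arm, set the trimmed share from the proportion with a post-visit score.

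**Cost.** A little more analysis work and wider stated uncertainty. No extra patients or data collection.

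**Optional.** MMIC and GOS could also be sent to non-attenders at a fixed time after the scheduled date. This changes the question to the combined effect of attendance and counselling. Exposure to the video could also differ by arm among non-attenders, because section 4.d sends it to telephone patients for viewing before or during the visit but shows it in session to in-person patients. At the example rates with 140 per arm, it means about 140 × 0.37 + 140 × 0.184 = 78 further surveys, with reminder calls, interpreter time and up to 78 × $15 = $1,170 in gift cards.
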